2. STUDY OBJECTIVES AND ENDPOINTS

2.1 Study Objectives

2.1.1 Primary Objective

Test the hypothesis that intravenous (IV) delivery of MSCs improves coronary artery endothelial function (assessed by fractional flow reserve (FFR) and coronary flow reserve (CFR) at 6 months), systemic endothelial function (assessed by FMD and EPC-colony assay), and angina symptoms (assessed by Seattle Angina Questionnaire) in type 2 DM patients with symptomatic IHD compared to placebo.

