| DEFINITION OF ENDPOINTS | 
Primary Endpoint (Efficacy)
 
 - Change in Brachial artery FMD% assessed at 2-weeks 1-, 3-, and 6-months post-infusion compared to baseline. - Change in EPC-CFUs at 2-weeks, 1-, 3-, and 6-months post-infusion compared to baseline. 
Secondary Endpoints (Efficacy)
 
 - Cardiac catheterization angiography IFR, CFR and FFR measurements to assess coronary artery endothelial function at 6 months post-infusion - Target lesion lumen loss by QCA at 6 months post-infusion. - Endothelialization and stent site vessel healing parameters by OCT or IVUS. - Circulating angiogenic and inflammatory markers at 1-, 3-, and 6-months post-infusion. - Seattle Angina Questionnaire (SAQ) Angina Frequency and Quality of Life scales at 1-, 3-, and 6-months post-infusion 
Secondary Endpoints (Safety)
 
 - Incidence (at one (1) month post-infusion) of any treatment-emergent serious adverse events (TE-SAEs), defined as the composite of: death, non-fatal MI, stroke, hospitalization for heart failure, sustained ventricular arrhythmias (characterized by ventricular arrhythmias lasting longer than 30 sec or with hemodynamic compromise) or atrial fibrillation. - Incidence of Major Adverse Cardiac Events (MACE), defined as the composite incidence of (1) death, (2) hospitalization for cardiovascular events, or (3) non-fatal MI at 12 months. - Treatment emergent adverse event (AE) and serious adverse event (SAE) rates through the duration of the study. - Target Vessel Failure (revascularization, death, or MI attributed to the target vessel) post-PCI (only applicable if participant undergoes PCI). - Abnormal hematology and clinical chemistry value results. |
| Inclusion Criteria | 
 1. Be ≥ 18 years of age (males and females). 2. Provide written informed consent. 3. Have a diagnosis of symptomatic IHD and an indication for standard-of-care coronary angiography. 4. Have Type 2 diabetes mellitus documented by hemoglobin A1C $> 7\%$, or on medical therapy for Type 2 diabetes mellitus. |

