2.2.2. Secondary Endpoints

Efficacy:

- Cardiac catheterization angiography, CFR and FFR measurement to assess post-coronary angiography coronary artery endothelial function at 6 months post-infusion
- Target lesion lumen loss by QCA at 6 months post-infusion
- Endothelialization and stent site vessel healing parameters by OCT (only applicable if participant undergoes PCI).
- Circulating angiogenic and inflammatory markers at 1-, 3-, and 6-months post-infusion.
- Seattle Angina Questionnaire (SAQ) Angina Frequency and Quality of Life scales at 1-, 3-, and 6-months post-infusion.

Safety:

- Incidence (at one (1) month post-infusion) of any treatment-emergent serious adverse events (TE-SAEs), defined as the composite of: death, non-fatal MI, stroke, hospitalization for heart failure, sustained ventricular arrhythmias (characterized by ventricular arrhythmias lasting longer than 30 sec or with hemodynamic compromise) or atrial fibrillation.

- Incidence of Major Adverse Cardiac Events (MACE), defined as the composite incidence of (1) death, (2) hospitalization for cardiovascular events, or (3) non-fatal MI at 12 months.
- Treatment emergent adverse event (AE) and serious adverse event (SAE) rates through the duration of the study.
- Target Vessel Failure (revascularization, death, or MI attributed to the target vessel) post-PCI (only applicable if participant undergoes PCI).
- Abnormal hematology and clinical chemistry value results.

Exploratory:

- Detailed molecular and functional assessment (genomic, proteomic, proliferation, senescence and differentiation, and angiogenic assays) of bone marrow aspirate at 3 months post-infusion.

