2. A physical examination will be performed and may include the following examinations: general appearance; skin and nails; limbs; head, eyes, ears, nose, throat (HEENT) and neck; respiratory; cardiovascular; and abdominal. Vital Signs measurements will consist of: height, weight, heart rate, blood pressure, respiratory rate, oxygen saturation, and temperature. Height is only required at screening. If physical exam and vitals were performed as “Standard of Care” within 7 days of signing ICF, those results may be extracted from patient medical records and used for the screening visit in this study. The screening visit physical exam can be completed by the participants’ treating physician.
3. Concomitant medications will be recorded at screening visit and updated at each visit.
4. Randomization can be performed within 7 days prior to IP infusion.
5. Refer to Appendix 1 for Infusion guidelines.
6. Refer to hospital protocols for coronary angiogram guidelines. Results from the screening cardiac catheterization may be extracted from patient medical records and used for the purposes of this study. Subjects who did not have a stent placed at screening will not undergo the coronary angiogram (and associated measurements) at Month 6, but should complete the other assessment listed on Time and Events Table, per investigator’s judgement.
7. Subjects who did not have a stent placed at screening may still undergo the coronary angiogram (and associated measurements) at Month 6, but should complete the other assessment listed on Time and Events Table. All procedures (CFR, FFR, IFR, IVUS, and/or OCT) will be performed in accordance with the established hospital protocols which are done as “Standard of Care”. Subjects who undergo PCI at screening should have CFR, FFR, IFR, IVUS, and/or OCT measurements if available, as per investigator’s judgement.
8. Refer to Appendix 2 for Brachial Ultrasound (Brachial Artery Ultrasound to assess endothelial function must be performed prior to 12pm).
9. Bone Marrow Biopsy will be performed at month 3 visit. Separate ICF will be used for this optional sub-cohort. The bone marrow biopsy can be performed in the Catheterization Laboratory or in Interventional Radiology department, either with or without imaging guidance (X-Ray or Ultrasound).
10. All subjects will be asked to complete the Seattle Angina Questionnaire (SAQ), EQ-5D, and SF-36 quality of life questionnaires. Only male subjects will be asked to

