8.1 Screening Visit

See Table 1 for the procedures and assessment to be performed during the screening visit of the study. Screening visit can take place within 7 days before or after coronary angiogram. All screening visit test and procedures will occur upon signing the informed consent form (ICF). No screening exams will take place until the subject is fully informed of the research and signs the consent form.

A subject may be rescreened based on the Investigators judgement and will at a minimum need to reconsent and complete screening laboratory tests. The subject will remain with the same subject number throughout this process.

If any of the screening assessments (coronary angiogram, vasoreactivity testing, OCT, physical exam, labs, EKG, etc.) were performed as “Standard of Care” within 7 days of signing ICF, those results may be extracted from patient medical records and used for the screening visit in this study.

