8.2 Baseline and Day 0 Visit

See Table 1 for the procedures and assessment to be performed during the baseline visit of the study. This visit will occur after all screening tests are completed and it has been determined that the subject meets eligibility criteria. This visit should occur within 0 - 30 days post-coronary angiogram.

See Table 1 for the procedures and assessment to be performed during the Day 0 visit of the study. The Day 0 visit will occur within 0 - 30 days post-coronary angiogram after all baseline tests are completed and it has been determined that the subject remains eligible. Once the subject is deemed eligible to continue in the study, the subject will be administered the investigational product. Refer to Appendix 1 for Infusion Guidelines.

8.3 Week 2, Month 1, Month 3, Month 6, and Month 12 (Post-Infusion Visit)

See Table 1 for the procedures and assessment to be performed for the Week 2, Month 1, Month 3, Month 6, and Month 12 study visits. Subjects who had a stent placed at screening will have a follow up coronary angiography at 6 months post-investigational product infusion to evaluate the treated lesion lumen loss with quantitative coronary angiography (QCA), physiology with fractional flow reserve (FFR) and endothelial function with coronary flow reserve (CFR). Outpatient visits should be completed as close to the scheduled visit dates as possible. There will be a window of ± 5 days for week 2 and ± 2 weeks for the Month 1, 3, 6, and 12 study visits.

An optional sub-study will be conducted on at least 5 participants from each treatment group in which they will undergo a bone marrow biopsy at Month 3 for a detailed molecular (genomic, proteomic, proliferation, senescence and differentiation assays) and functional assessment (angiogenic assays) of the effect of allogeneic MSCs on bone marrow derived autologous MSC and EPCs. All subjects will be asked to sign a separate ICF before participating in this optional sub-study. Due to the blinded nature of the study, more than 10 subjects will be enrolled in this sub-study and Cell Manufacturing lab will inform the clinical team once 5 subjects from each treatment complete the bone marrow biopsy. In the interest of participant safety, the bone marrow biopsy may be performed under ultrasound guidance (X-Ray or Ultrasound) by interventional radiology department, if indicated by investigator's clinical judgement.

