8.4.4 Coronary Angiography

Coronary angiography will be done by the interventional cardiologist 6 months after infusion of the investigational product to assess post-PCI coronary artery endothelial function, assessed by IFR, CFR, and/or FFR, as available. Participants will also have evaluation of target lesion lumen loss by IVUS or OCT, as available.

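### The protocol contradicts itself on whether FFR measures coronary endothelial function, so a patency difference at Month 6 could be read as a coronary endothelial effect

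*Combined protocol and SAP*

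**What the plan says.** Five places give FFR the role of an endothelial measure:

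- Section 2.1.1, and the synopsis objective in matching words, test whether treatment "improves coronary artery endothelial function (assessed by fractional flow reserve (FFR) and coronary flow reserve (CFR) at 6 months".
- Section 2.2.2 lists as a secondary endpoint "CFR and FFR measurement to assess post-coronary angiography coronary artery endothelial function at 6 months post-infusion". IFR is not named there.
- The synopsis version of that endpoint adds IFR: "Cardiac catheterization angiography IFR, CFR and FFR measurements to assess coronary artery endothelial function at 6 months post-infusion".
- Section 8.4.4 says the Month 6 angiogram is done "to assess post-PCI coronary artery endothelial function, assessed by IFR, CFR, and/or FFR, as available".

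Section 8.3 assigns the roles differently for the same Month 6 procedure. After QCA for lumen loss it lists "physiology with fractional flow reserve (FFR) and endothelial function with coronary flow reserve (CFR".

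On who is measured, 8.3 states: "Subjects who had a stent placed at screening will have a follow up coronary angiography at 6 months post-investigational product infusion". Note 6 to Table 1 agrees: "Subjects who did not have a stent placed at screening will not undergo the coronary angiogram (and associated measurements) at Month 6". Note 7 says that non-stented subjects may still have it. Table 1 marks the FFR/CFR/IFR/IVUS/OCT row as optional.

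The primary endpoints in 2.2.1 are FMD% and EPC-CFU only. Section 10.2 calls the efficacy outcomes exploratory, tests at a two-sided 0.05 level and makes no multiplicity adjustment. Section 10 says nothing about how FFR, IFR or CFR will be analysed or interpreted.

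**The concern.** The coronary hypothesis comes first in the primary objective, and the reader needs to know which measurement answers it. As written, the answer depends on the section: FFR or CFR (2.1.1, 2.2.2), any of IFR, CFR or FFR (8.4.4), or CFR alone (8.3).

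This matters because the indices are not interchangeable. FFR and IFR compare pressure beyond a lesion with aortic pressure, so they describe how far the epicardial vessel obstructs flow. Neither involves provoking the endothelium. In a group made up mainly of stented subjects, the arms may differ on FFR or IFR because lesion or stent patency differs. With no rule saying which index supports the endothelial conclusion, such a difference could be reported as an effect on the coronary endothelium, and a null result as its absence. The choice of index could also be made after the data are seen.

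**Working it through.** The documents give no value, SD, expected effect or power for any coronary index, so there is no figure to reproduce. The check has two parts.

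**1. The sections side by side**

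| Place | FFR | IFR | CFR |
|---|---|---|---|
| Synopsis objective; 2.1.1 | endothelial function | not named | endothelial function |
| Synopsis secondary endpoint | endothelial function | endothelial function | endothelial function |
| 2.2.2 | endothelial function | not named | endothelial function |
| 8.3 | physiology | not named | endothelial function |
| 8.4.4 | endothelial function, if available | endothelial function, if available | endothelial function, if available |

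Section 8.3 cannot be squared with the other rows on FFR. IFR appears in the synopsis endpoint, Table 1 and 8.4.4, but not in 2.1.1, 2.2.2 or 8.3.

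**2. An illustration of why the label matters**

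This model is an assumption and uses no figure from the protocol. Take an epicardial resistance Re in series with a microvascular resistance Rm, aortic pressure 100 and venous pressure 0, during maximal flow:

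- FFR = Rm / (Rm + Re)
- hyperaemic flow = 100 / (Rm + Re). This is the numerator of CFR, so CFR moves with it if resting flow is unchanged.

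Set Rm = 1 and vary Re:

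| Re | Baseline FFR; flow | Re halved (better patency) | Rm cut by 20% (lesion unchanged) |
|---|---|---|---|
| 0.05 | 0.952; 95.2 | 0.976; 97.6 | 0.941; 117.6 |
| 0.10 | 0.909; 90.9 | 0.952; 95.2 | 0.889; 111.1 |
| 0.25 | 0.800; 80.0 | 0.889; 88.9 | 0.762; 95.2 |

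Worked line for Re = 0.10:

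- Baseline FFR is 1/1.10 = 0.909.
- With the lesion resistance halved, FFR is 1/1.05 = 0.952.
- With microvascular resistance down 20%, FFR is 0.8/0.9 = 0.889, while flow goes from 100/1.10 = 90.9 to 100/0.9 = 111.1.

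In this model FFR rises with patency and falls when the microvessels open. Hyperaemic flow rises in both cases (90.9 to 95.2 when Re is halved), so CFR is only a partial endothelial measure. The model is written for FFR. IFR is also a distal-to-aortic pressure ratio but was not modelled.

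**The case against.** The strongest replies are these:

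- **Weight.** The coronary indices are secondary, optional and taken as available, efficacy is exploratory, and FMD% and EPC-CFU are primary. This stands and limits the point. It does not remove it, because coronary endothelial function is part of the primary objective and exploratory status does not settle what an index measures.
- **Patency data are planned.** QCA lumen loss is a separate secondary endpoint at the same procedure, and stent-site healing by OCT (or IVUS, in the synopsis) is another. This also stands: the data to check an FFR difference should largely exist. What is missing is any statement that they will be read together.
- **Patency may be part of the intended effect.** The background section hypothesises better vessel healing after PCI, so a patency difference between randomised arms could be a real treatment effect. That is fair, but it would be an effect at the lesion and should be reported as one.
- **The definition comes from outside the protocol.** No section says that FFR and IFR are pressure ratios. The point relies on that definition. The contradiction between 8.3 and the other sections does not.

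A reader might also infer more than the documents support:

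- That Month 6 FFR or IFR mainly shows the stent result, or has little room to move. The documents give no figure for either claim, and the resistances above are chosen values.
- That 8.4.4 creates a pooled endpoint in which IFR alone counts. It defines neither a composite nor a rule for who counts as assessed.
- That the vasoreactivity testing in 8.1 is the remnant of a dropped endothelial test. It appears once, in a list of screening results that may be taken from records ("coronary angiogram, vasoreactivity testing, OCT, physical exam, labs, EKG, etc"), and is not described as coronary or endothelial. It is a housekeeping mismatch with Table 1.

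**Conclusion.** The point holds as an internal contradiction with a consequence for interpretation. One section treats FFR as physiology. The objective, the secondary endpoint and the assessment section treat it as endothelial function, and two places add IFR to that label. Followed as written, the protocol allows a patency-driven difference in FFR or IFR to answer the coronary part of the primary objective.

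The effect is confined to that part. The primary endpoints are untouched, and nothing in the documents allows the size of any misreading to be estimated. The conclusion assumes the standard definition of FFR and IFR as pressure ratios, and a Month 6 group that is mainly stented, as 8.3 and note 6 indicate. Note 7 leaves room for others, and the two notes need to be reconciled. It is worth correcting before analysis because it changes what the trial can conclude about the coronary arteries.

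**What to change.** Wording changes only, with no new procedure:

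1. In the synopsis objective and endpoint, 2.1.1, 2.2.2 and 8.4.4, follow 8.3 and label FFR (and IFR where it is listed) as epicardial or target-vessel physiology.
2. Define FFR, IFR and CFR as separate endpoints in place of the and/or wording, each reported with the number of subjects measured per arm and alongside QCA lumen loss.
3. State that a result on FFR or IFR alone will not support a conclusion on coronary endothelial function.
4. Let CFR carry the coronary hypothesis, described as coronary vasodilator reserve and only a partial endothelial measure. Add that qualification in 8.3 too. Keep FMD% and EPC-CFU for systemic endothelial function, the role 2.1.1 gives them. Resting the coronary conclusion on them would leave the coronary hypothesis without a measure.
5. Reconcile the IFR listing between the synopsis and the body, notes 6 and 7 to Table 1, and the vasoreactivity entry in 8.1 with Table 1.

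The cost is a protocol and analysis-plan amendment and a narrower coronary claim.

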2.1.2 Secondary Objectives

Test the hypothesis that allogeneic MSCs promote endothelial repair through rescue of bone marrow progenitors in type 2 DM patients with symptomatic IHD compared to placebo.

2.2 Study Endpoints

2.2.1 Primary Endpoints (Efficacy)

- Change in Brachial artery FMD% assessed at 2 weeks, 1-, 3-, and 6-months post-infusion compared to baseline.
- Change in EPC-CFUs at 2 weeks, 1-, 3-, and 6-months post-infusion compared to baseline.

2.2.2. Secondary Endpoints

Efficacy:

- Cardiac catheterization angiography, CFR and FFR measurement to assess post-coronary angiography coronary artery endothelial function at 6 months post-infusion
- Target lesion lumen loss by QCA at 6 months post-infusion
- Endothelialization and stent site vessel healing parameters by OCT (only applicable if participant undergoes PCI).
- Circulating angiogenic and inflammatory markers at 1-, 3-, and 6-months post-infusion.
- Seattle Angina Questionnaire (SAQ) Angina Frequency and Quality of Life scales at 1-, 3-, and 6-months post-infusion.

Safety:

- Incidence (at one (1) month post-infusion) of any treatment-emergent serious adverse events (TE-SAEs), defined as the composite of: death, non-fatal MI, stroke, hospitalization for heart failure, sustained ventricular arrhythmias (characterized by ventricular arrhythmias lasting longer than 30 sec or with hemodynamic compromise) or atrial fibrillation.

- Incidence of Major Adverse Cardiac Events (MACE), defined as the composite incidence of (1) death, (2) hospitalization for cardiovascular events, or (3) non-fatal MI at 12 months.
- Treatment emergent adverse event (AE) and serious adverse event (SAE) rates through the duration of the study.
- Target Vessel Failure (revascularization, death, or MI attributed to the target vessel) post-PCI (only applicable if participant undergoes PCI).
- Abnormal hematology and clinical chemistry value results.

Exploratory:

- Detailed molecular and functional assessment (genomic, proteomic, proliferation, senescence and differentiation, and angiogenic assays) of bone marrow aspirate at 3 months post-infusion.

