| STUDY OBJECTIVES | 
Test the hypothesis that intravenous (IV) delivery of MSCs improves coronary artery endothelial function (assessed by fractional flow reserve (FFR) and coronary flow reserve (CFR) at 6 months), systemic endothelial function (assessed by FMD and EPC-colony assay), and angina symptoms (assessed by Seattle Angina Questionnaire) in type 2 diabetic patients with symptomatic IHD compared to placebo.
 
Test the hypothesis that allogeneic MSCs promote systemic and coronary endothelial repair through rescue of bone marrow progenitors in type 2 diabetic patients with symptomatic IHD compared to placebo.
 |
| STUDY DESIGN | Randomized, Double Blind, Placebo controlled, Pilot Trial |
| INVESTIGATIONAL PLAN | 
30 type 2 diabetic patients with symptomatic IHD that undergo standard-of-care coronary angiography with or without Percutaneous Coronary Intervention (PCI) and meet all the inclusion and none of the exclusion criteria will be randomized to receive, within 2 weeks post- standard-of-care coronary angiography , either allogeneic MSCs or placebo in a 1:1 blinded fashion:
 
Group A (15 subjects): Allogeneic MSCs Fifteen (15) subjects will be treated with a single administration of intravenous allogeneic hMSCs (100 million).
 
Group B (15 subjects): Placebo (Cell-free PlasmaLyte-A medium supplemented with 1% HSA) Fifteen (15) subjects will be treated with intravenous placebo infusion.
 
 - Patients will be followed for scheduled outcome and safety assessments at 1, 3 and/or 6 months and 12 months post-infusion. - A bone marrow biopsy will be obtained from participants in a sub-study at the 3-month follow up for cellular and molecular studies (separate informed consent document). |
| ROUTE OF ADMINISTRATION | Peripheral Intravenous Infusion |
| DURATION OF STUDY PARTICIPATION | 12 months |
| SUBJECT POPULATION | 30 subjects age >18 with type 2 diabetes and symptomatic IHD with an indication for standard-of-care coronary angiography with or without PCI |

| | |
|-------------------------|---|

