damaged endothelial cells by stem/progenitor cells could allow reendothelialization, as well as neovascularization of ischemic tissues.

Follow-up coronary angiography after PCI is commonly implemented to assess the efficacy and safety of new revascularization devices and novel therapies. However, in clinical practice, routine follow-up coronary angiography has not been considered indicated in stable or asymptomatic post-PCI patients because the direct clinical benefits have been poorly defined. To address this question, Misumida et. al.[48], conducted a systematic review and meta-analysis of randomized trials to assess the potential clinical benefits associated with routine follow-up angiography post-PCI. They compared clinical outcomes after PCI between patients who underwent routine follow-up coronary angiography and those who only had clinical follow-up. Five randomized trials, totaling 4,584 patients met the inclusion criteria, including studies that used sub-randomization and ones that assigned consecutive patients per study protocol. The results showed that routine follow-up coronary angiography was associated with a lower rate of myocardial infarction (odds ratio [OR] 0.65; 95% confidence interval [CI] 0.46–0.91; $P=0.01$) without reduction in all-cause mortality (OR 0.87; 95% CI 0.59–1.28; $P=0.48$), and a higher rate of target lesion revascularization (OR 1.73; 95% CI 1.42–2.11; $P<0.001$). The investigators concluded that further studies investigating the potential role of routine follow-up angiography may be warranted.

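### Target Vessel Failure is timed from PCI and takes in any target-vessel revascularization, so it counts pre-infusion events and those prompted by the study's own Month 6 angiogram

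*Combined protocol and SAP*

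**What the plan says.** The synopsis and section 2.2.2 (Safety) word the endpoint identically: "Target Vessel Failure (revascularization, death, or MI attributed to the target vessel) post-PCI (only applicable if participant undergoes PCI"). No start at infusion or randomization is given, no end of follow-up, and no condition on why a revascularization was done. Section 10 adds no rule for it. The first safety endpoint in the same list is anchored to infusion: "Incidence (at one (1) month post-infusion) of any treatment-emergent serious adverse events (TE-SAEs").

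On timing, section 8.2 states "The Day 0 visit will occur within 0 - 30 days post-coronary angiogram after all baseline tests are completed", and Table 1 gives the same 0 to 30 days. The synopsis instead has treatment given "within 2 weeks post- standard-of-care coronary angiography". Footnote 4 to Table 1 allows randomization up to 7 days before infusion.

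On the second angiogram, section 8.3 states "Subjects who had a stent placed at screening will have a follow up coronary angiography at 6 months" after infusion. Footnote 1 to Table 1 calls only the first angiogram clinically indicated. Section 1.1 says that routine follow-up angiography has not been regarded as indicated in stable patients after PCI. It cites a meta-analysis that found "a higher rate of target lesion revascularization (OR 1.73"; 95% CI 1.42 to 2.11). The same sentence reports less MI (OR 0.65, 95% CI 0.46 to 0.91).

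**The concern.** A safety endpoint should count what happens after exposure and should let a reader separate product-related events from those the study procedures generate. This definition does neither. A target-vessel MI or repeat revascularization between the screening PCI and the infusion meets it before any product is given. So does a target-vessel revascularization done only because the Month 6 study angiogram showed a lesion. Nearly everyone to whom the endpoint applies is scheduled for that angiogram.

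With 15 subjects per arm, and fewer with PCI, one or two such events can dominate the tabulation. TVF is the only clinical endpoint in the list that is specific to the treated vessel, and the DSMB reviews safety data by group (11.3). The counts therefore need to be readable.

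**Working it through.** The plan gives no event rate, power or expected count for TVF, so there is no stated figure to reproduce. The figures below are illustrative.

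**1. Pre-infusion share of observation.** Inputs: a gap g of at most 14 days (synopsis) or 30 days (8.2, Table 1), and follow-up to Month 12, taken as 365 days because TVF has no stated horizon. Share = g / (g + 365).
- g = 14: 14/379 = 3.7%
- g = 30: 30/395 = 7.6%

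These are upper limits. Only randomized subjects are counted, so a death before randomization cannot enter. What can enter is an MI or repeat revascularization after PCI, plus any component event in the up to 7 days between randomization and infusion. Section 8.2 rechecks eligibility before Day 0, but no listed exclusion names a recent MI or repeat PCI. Removal would rest on investigator judgement.

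**2. Revascularizations attributable to routine angiography.** Inputs: OR 1.73 (1.42 to 2.11) from section 1.1, and an assumed rate p without routine angiography, which the documents do not give. With odds = OR × p/(1 − p), the rate with routine angiography is q = odds/(1 + odds), and the excess share is (q − p)/q. Example at p = 10%: 0.1111 × 1.73 = 0.1922; 0.1922/1.1922 = 16.1%; (16.1 − 10)/16.1 = 38%.

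| Assumed p | q at OR 1.73 (over the CI) | Excess share at OR 1.73 (over the CI) |
|---|---|---|
| 5% | 8.3% (7.0 to 10.0) | 40% (28 to 50) |
| 10% | 16.1% (13.6 to 19.0) | 38% (27 to 47) |
| 15% | 23.4% (20.0 to 27.1) | 36% (25 to 45) |
| 20% | 30.2% (26.2 to 34.5) | 34% (24 to 42) |

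**3. In events.** The number with PCI is not stated. Assuming 10 per arm and p = 10%, expected revascularizations per arm rise from 10 × 0.10 = 1.0 to 10 × 0.161 = 1.6. The chance of at least one rises from 1 − 0.90^10 = 65% to 1 − 0.839^10 = 83%.

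**4. Does other text remove these events?** The note in 9.6 on elective hospitalization and the exclusion of procedures in 9.3 limit what is an adverse event. Neither alters the TVF definition, and section 10.1 says only that all randomized subjects are summarized for safety.

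**The case against.** Several points on the other side stand.

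- The same meta-analysis reports fewer MIs with routine angiography, and MI is a TVF component. A reader might infer that the Month 6 angiogram raises the TVF rate overall. The documents do not show this. The cited OR also concerns the target lesion, whereas the endpoint concerns the target vessel.
- Both arms follow the same schedule under blinding. A reader might infer bias, or a diluted difference between arms. Neither is demonstrated: if routine angiography multiplies the odds equally in both arms, the between-arm odds ratio is unchanged. Restenosis found at Month 6 may also reflect treatment, since lumen loss and stent-site healing are trial endpoints. These events should be shown separately, not discarded.
- Because applicability is not expressly limited to the screening PCI, a reader might infer that a first PCI during follow-up brings a subject into the denominator and breaks the randomized comparison. That reading is strained. The synopsis describes entry angiography with or without PCI, footnote 7 speaks of PCI at screening, and section 8.3 of a stent placed at screening. The index PCI is the natural meaning; a few words would settle it.
- The revascularization component is limited to the target vessel, so other vessels are not swept in.
- The MACE component "2) hospitalization for cardiovascular events" does not naturally cover an admission solely for a scheduled study angiogram. The adverse-event text does not settle the matter for MACE, so such a case should be flagged, but it is a minor strand.
- It is tempting to add that PCI complications cluster in the pre-infusion weeks. Nothing in the documents says so, and the point does not need it.

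What remains unanswered is the clock, and the lack of any record of why a revascularization was done.

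**Conclusion.** The point holds in limited form. As written, TVF counts target-vessel events before exposure and target-vessel revascularizations prompted by a study procedure as safety outcomes of the product. The first part is small: at most 3.7% or 7.6% of observation, depending on which interval governs. The second could be about 36% to 40% of revascularizations at base rates of 5% to 15%, or 25% to 50% over the CI (down to 24% at a 20% base rate). This rests on assumed base rates, on carrying a target-lesion odds ratio over to the target vessel, and on reading the excess as angiogram-prompted. The net effect on the composite is not known.

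The consequence is mixed, hard-to-interpret counts in a 30-subject pilot with no formal sample-size basis. The documents support neither a directional bias nor a compromised comparison. The endpoint is secondary, but the wording should be corrected because the repair is cheap.

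**What to change.** - In the synopsis and section 2.2.2, define TVF in subjects who had PCI at the screening catheterization, with onset from infusion to Month 12.
- List events between PCI and infusion separately, split into before and after randomization, so that no post-randomization event is lost. Events in subjects randomized but never infused belong in the after-randomization part.
- Record the reason for each revascularization on the CRF.
- Report TVF twice: with and without target-vessel revascularizations first prompted only by the protocol Month 6 angiogram or by the physiology measured at it. An abnormal physiology result from that procedure must not by itself move an event into the restricted count.
- Flag in the same way any MACE hospitalization arising solely from that angiogram.
- Reconcile the synopsis interval from angiogram to infusion with that in section 8.2 and Table 1.

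The cost is endpoint wording, one CRF item, one extra tabulation and slightly fewer events in the restricted count. Patient care does not change.
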